2.2.3 Melanoma Patients: Checkpoint Inhibitor Experienced

Ipiliumumab was the first checkpoint inhibitor approved for use in unresectable or metastatic melanoma based on significant improvement in overall survival shown in a pivotal randomized double-blind Phase III study (Hodi et al 2010). Subsequent to this, nivolumab was approved in advanced melanoma patients without *BRAF* mutation (Robert et al 2015). Pembrolizumab was approved for treatment of patients with advanced or unresectable melanoma who progressed after ipilimumab and/or *BRAF* therapy (Ribas et al 2015; Robert et al 2015).

The combination of ipilumumab and nivolumab has recently received approval in previously untreated patients with unresectable or metastatic melanoma (Robert et al 2015), although toxicity may be more prominent with the combination therapy. An analysis involving patients with a PD-L1 expression level of more or less than 1%, suggests that this biomarker may determine the best option for individual patients, as monotherapy may provide sufficient results in terms of survival with less toxicity (Larkin et al 2015; Wolchok et al 2017).

2.2.4 Esophageal Squamous Cell Carcinoma Patients: Checkpoint Inhibitor Naïve

Treatment in esophageal squamous cell carcinoma (ESCC) patients without distal metastases is aimed at a radical cure by methods appropriate for their stage of cancer. Meanwhile, for patients with distal metastases or those with a postoperative distant recurrence, combination therapy with platinum based chemotherapy and 5-FU (FP therapy) is recommended as the standard treatment. In the second-line setting, singleagent chemotherapy is an established option based on patient benefit-risk assessment (Lordick et al 2016, Muro et al 2019, National Comprehensive Cancer Network 2019, Kitagawa et al 2019). Although second-line treatments with docetaxel and paclitaxel are used for patients with advanced ESCC that has progressed after first-line chemotherapy. they are associated with hematological, gastrointestinal, and neurological toxicities (Jimenez et al 2011) and with poor long-term survival (Kato et al 2011, Muro et al 2004). More recently pembrolizumab has been approved for second-line therapy for ESCC, with PD-L1 expression levels by CPS of ≥ 10. Similarly, nivolumab has shown positive Phase III data in second-line ESCC independent of PD-L1 expression (Kato et al 2019) which has led to the approval of nivolumab for the treatment of patients with unresectable advanced or recurrent esophageal cancer that has progressed following chemotherapy in Japan.

2.2.5 Targeting PD-1 and TIM-3 Antigens

Although patients with advanced NSCLC and melanoma can benefit from CPI therapy, many patients will progress. Therefore, new agents are needed to increase the proportion of responding patients, and ultimately improve survival. Several hypotheses exist for mechanisms of acquired resistance, such as acquisition of mutations which make tumors less susceptible to T-cell mediated killing through a loss of interferon gamma (IFNγ) response elements or MHC Class I (Zaretsky et al 2016). PD-1 is a checkpoint inhibitor that identifies activated and/or exhausted T-cells including tumor infiltrating CD8+ T-cells that recognize mutated tumor antigens (neo-antigens) through their T-cell receptor (TCR). Up-regulation of additional inhibitory surface membrane immune checkpoint proteins has been described following anti-PD-1 treatment. TIM-3 represents one such molecule co-expressed with PD-1 and induced by PD-1 blockade. PD-1 and TIM-3 expression correlate with the degree of impairment of tumor infiltrating lymphocytes (TILs), effector functions and, consequentially, with a poor prognosis.

TIM-3 is an emerging checkpoint inhibitory molecule involved in the regulation of antitumor immunity that is expressed on T-cells and innate immune cells (e.g., macrophages, dendritic, and natural killer (NK) cells), where it has been shown to suppress their responses upon interaction with their ligands (Anderson et al 2016; Das et al 2017). Recently, the results of a Phase I study of TSR-022, an anti–TIM-3 mAb, were reported for patients with advanced solid tumors (Weiss et al 2017). Overall, TSR-022 monotherapy was well tolerated across multiple dose levels. Adverse events were manageable and consistent with the safety profiles of other CPIs.

The role of the co-expression of PD-1 and TIM-3 has been found on TILs in inflamed tumors with an ongoing antigen-specific immune response against the tumor, including melanoma and NSCLC (Gros et al 2014; Thommen et al 2015). PD-1 and TIM-3 can be found up-regulated upon treatment with T-cell BsAbs. In mouse models, combined targeting of the PD-1 and TIM-3 pathways has been shown to be more effective in controlling tumor growth of syngeneic mouse tumors than targeting either pathway alone (Sakuishi et al 2010). Similarly, during chronic viral infection, the dual blockade of PD-1 and TIM-3 enhanced the function of exhausted virus-specific CD8 T-cells (Jin et al 2010). Indeed, preclinical experiments in PD-1–resistant tumors and analysis of patient tumor samples showed that TIM-3 can act as a marker and seems to have a role in the mechanism to evade immune response to anti–PD-1/PD-L1 therapy (Koyama et al 2016). Nevertheless, despite evidence in the literature, the exact mechanism for how TIM-3 interferes with anti-tumor immune response and the interaction with its putative ligands (e.g., Galectin-9, CEACAM-1, HMGB1 or phosphatidylserine) is not fully understood.

[figure not shown]
2.2.6 Description of RO7121661

RO7121661 is a novel, Fc-silent IgG1-based BsAb in the 1+1 format that incorporates monovalent binding to each of both checkpoint receptors, PD-1 and TIM-3. Use of a natural IgG-like monovalent heterodimeric IgG1 format allows avidity for simultaneous binding to PD-1 and TIM-3 when both receptors are co-expressed. RO7121661 binds with monovalent high affinity to a glycopeptide-epitope on PD-1, and with low affinity to TIM-3 to induce an avidity driven selectivity effect for binding to T-cells in the tumor microenvironment that co-express both PD-1 and TIM-3 or to T-cells expressing PD-1 alone. This preferential binding avoids the targeting of other TIM-3 expressing cells such as myeloid or NK cells.

An additional feature of RO7121661 is the specifically engineered IgG1-based Fc-region that prevents binding to Fc γ Rs by introduction of PGLALA mutations (Kabat et al 1991; Schlothauer et al 2016). This may avoid tumor-associated macrophage resistance mechanisms, which have been observed with IgG4-based PD-1 antibodies such as pembrolizumab and nivolumab (Arlauckas et al 2017). A schematic of the antibody is shown in Figure 2.

A detailed description of the chemistry, pharmacology, and safety of RO7121661 is provided in the RO7121661 Investigator's Brochure (IB).

Figure 2 Schematic Representation of the RO7121661 Bispecific Antibody

Crossed PD-1 heavy chain (HC1=A), crossed PD-1 light chain (LC1=C), uncrossed TIM-3 light chain (LC=D), and TIM-3 heavy chain (HC2=B). PD-1=programmed death-1; TIM-3=T-cell immunoglobulin and mucin domain 3.

2.3 BENEFIT/RISK ASSESSMENT

Benefit from cancer immunotherapy (CIT) with CPI mAbs, such as those targeting PD-1/PD-L1, is predominantly observed in a subset of patients with inflamed tumor phenotypes. However, response is not guaranteed even in this patient subset due to either primary or acquired resistance mechanisms. Upregulated TIM-3 expression on T-cells is associated with T-cell dysfunction potentially resulting in baseline or acquired resistance to anti-PD-1/PD-L1 therapies (Koyama et al 2016). Therefore, TIM-3 blockade may overcome or prevent resistance mechanisms to anti-PD-1/PD-L1 and help restore cytotoxic T-cell proliferation and enhance T-cell function. RO7121661, a novel IgG1-based BsAb that targets the CPI receptors PD-1 and TIM-3, may serve to overcome such resistance through ligand blockade and subsequent T-cell re-invigoration and/or potentially prevent or delay the development of resistance.

Compared to monospecific PD-1/PD-L1 directed antibodies, one might expect a similar safety profile, but better efficacy primarily coming from targeting both PD-1 and TIM-3 mediated immune resistance mechanisms. The reduction of drug internalization may also result in improved clinical pharmacology characteristics compared to monospecific antibodies. Compared to monospecific PD-1/PD-L1 and TIM-3 antibody combinations or other PD-1/TIM-3 bi-specifics, one anticipates similar efficacy in the context of better safety due to the preferential targeting of TILs, sparing of the myeloid compartment with avoidance of a peripheral sink, and lack of effector function due to the PGLALA mutation in the Fc region.

As the mechanisms for optimal targeting of immune regulation in the tumor environment are still under exploration, rational new approaches to increase response rates to first line CPI therapy are warranted. Untreated NSCLC patients who demonstrate TPS or PD-L1 \geq 50%, which has clearly demonstrated sensitivity to PD-1 targeting, may benefit from first line treatment with a PD-1/TIM-3 BsAb if in fact the additional targeting of TIM-3 leads to additive antitumor activity beyond that expected of PD-1 targeting alone.

RO7121661 has demonstrated single-agent activity in Part A of this study. As of 1 March 2020, objective responses with long-lived partial remissions were achieved in one participant with metastatic ESCC and one participant with metastatic non-small cell lung adenocarcinoma. Of note, the non-small cell lung adenocarcinoma participant was previously treated with a PD-L1 inhibitor and had PD as best overall response on this treatment. Further, disease control with disease stabilization or minor response was achieved in other solid tumor types with an overall disease control rate (DCR) of 35.9% (14/39 patients).

RO7121661 was well tolerated in the patients dosed in Part A of this study. No specific safety concerns were identified and no MTD was identified although 1 DLT (Grade 3 Troponin T increased, unresolved at the time of the publication of this version of protocol) was observed at 1.2 g dose level.

Precaution against general risks for patients have been taken into account in the safety measures for this study, which include the definition of the inclusion/exclusion criteria (Section 5), dose-limiting toxicities (DLTs; Section 4.1.3), and rules for treatment interruption and withdrawal from study (Section 7).

The re-invigorating action of RO7121661 on immune effector cells, particularly given the TIM-3 modulation, might bear the risk of exaggerated immune cell activation that may result in the occurrence of enhanced, untoward, immune-mediated adverse events (imAEs) and an increase in cytokine release-mediated toxicities. Recommendations for the prophylaxis and the management of specific and known PD-1/PD-L1-mediated adverse events (AEs) can be found in Section 8.3.8 and Appendix 6.

Administration of therapeutic antibodies may cause infusion-related reactions (IRRs), which may include symptoms such as fever, chills, hypotension, shortness of breath, skin rash, headache, nausea, and vomiting. Such reactions typically occur during or shortly after the infusion, predominantly the first infusion. The incidence and severity typically decrease with subsequent infusions. Based on in vitro data, the risk of pro-inflammatory cytokine mediated IRRs upon first administration of RO7121661 as single agent is considered low. The recommended management of IRRs is detailed in Section 8.3.8.1.

Administration of therapeutic antibodies may cause the formation of ADAs, which may negatively affect the safety of the therapeutic (e.g., allergic reactions, immune

complex-mediated diseases). In the non-GLP DRF PK/PD study and the 4-week GLP study in cynomolgus monkeys, ADA development was observed independently of the dose groups (RO7121661 IB Section 4.2.2.1 and Section 4.2.3.1). No adverse findings were observed; no toxicity related to ADA formation was observed.

More detailed information about the known and expected benefits in the context of potential risks and reasonably expected adverse events of RO7121661 is provided in the RO7121661 IB.

Based on the considerations above, currently available data from Part A of this study and the planned safety monitoring and management guidance, the proposed study treatment is considered to have an appropriate benefit/risk profile for the population included in this study.

COVID-19 Benefit/Risk Assessment

In the setting of the coronavirus disease (COVID-19) pandemic, patients with comorbidities (including those with cancer) are a more vulnerable population. Infection with sudden acute respiratory syndrome coronavirus 2 (SARS-CoV-2) has been associated with higher morbidity and mortality in patients with cancer in some retrospective analyses. It is unclear how immunotherapy affects the incidence or severity of COVID-19. It is not anticipated that treatment with RO7121661 will increase the risk of infection with SARS-CoV-2. Severe COVID-19 is associated with a cytokine release syndrome (CRS) involving the inflammatory cytokines IL-6, IL-10, IL-2, and interferon-gamma. RO7121661 has a low risk of CRS and, while it is not known, there may be a potential for an increased risk of an enhanced inflammatory response if a participant develops SARS CoV-2 infection while receiving RO7121661. At this time, there is insufficient evidence for causal association between RO7121661 and an increased risk of severe outcomes from COVID-19.

There are limited data concerning the possible interactions between cancer immunotherapy treatment and SARS-CoV-2 vaccination, and it is recognized that human immune responses are highly regulated and that immune-modifying therapies may positively or negatively impact the efficacy and safety of SARS-CoV-2 vaccination (Society for Immunotherapy for Cancer [SITC] 2020).

Per recommendations of the National Cancer Comprehensive Network (NCCN) COVID-19 Vaccination Advisory Committee, SARS-CoV-2 vaccination is recommended for all patients with cancer receiving active therapy (including immune checkpoint inhibitors), with the understanding that there are limited safety and efficacy data in such patients (NCCN 2021). Given the lack of clinical data, currently no recommendations can be made regarding the optimal sequence of SARS-CoV-2 vaccination in patients who are receiving cancer immunotherapy (SITC 2020). For patients enrolling in this study and receiving RO7121661, a decision to administer the

vaccine to a patient should be made on an individual basis by the Investigator in consultation with the patient.

In alignment with clinical practice procedures, factors to consider when making the individualized decision for patients receiving RO7121661 to receive SARS-CoV-2 vaccination include the following: the risk of SARS-CoV-2 infection and potential benefit from the vaccine, the general condition of the patient and potential complications associated with SARS-CoV-2 infection, underlying disease, and the severity of COVID-19 outbreak in a given area or region.

SITC and NCCN recommendations along with institutional guidelines should be used by the Investigator when deciding on administering SARS-CoV-2 vaccines. When administered, SARS-CoV-2 vaccines must be given in accordance with the approved or authorized vaccine label. Receipt of the SARS-CoV-2 vaccine is considered a concomitant medication and should be documented as such (see Section 6.5).

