A DLT is defined as a clinically significant AE (classified according to the National Cancer Institute Common Terminology Criteria for Adverse Events [NCI CTCAE] v.5.0, as applicable) or significant laboratory abnormality: 1) occurring during the DLT assessment period of 21 days from the start of the first RO7121661 administration; 2) considered to be related to study treatment RO7121661 by the Investigator and; 3) is not attributed to disease progression or another clearly identifiable cause.

Investigators are encouraged to perform additional tests to determine the underlying etiology and most appropriate attribution.

For the purpose of this study the following AEs are considered DLTs:

- Hematological toxicities:
 - Grade 4 neutropenia (ANC $< 0.5 \times 10^9$ /L) lasting > 5 days.
 - Grade ≥ 3 febrile neutropenia associated with single body temperature > 38.3°C or sustained body temperature ≥ 38°C for > 1 hour, and/or with infection.
 - Grade 4 thrombocytopenia lasting>48 hours.
 - Grade 3 thrombocytopenia associated with bleeding episodes requiring a platelet transfusion.
 - Grade 4 anemia
 - Grade ≥ 3 anemia with hemolysis
- Any non-hematological toxicity of Grade ≥ 3 including:
 - Any Grade 3 immune-mediated AE.
 - Grade 3 hyperbilirubinemia lasting for > 48 hours or Grade 4 hyperbilirubinemia.

- Grade≥3 AST or ALT elevations with hyperbilirubinemia of Grade≥2.
- Grade 4 AST or ALT elevations.
- Grade ≥ 3 nausea, vomiting, or diarrhea despite maximal supportive treatment.
- Grade ≥ 3 non-hematological laboratory abnormality requiring medical treatment/intervention or hospitalization.
- The following Grade ≥ 3 non-hematological toxicity are exceptions for consideration as DLTs:
 - Alopecia (any grade).
 - Grade 3 nausea or vomiting that resolves to Grade ≤ 1 with or without supportive therapy within one week.
 - Grade 3 hypophosphatemia resolved within one week.
 - Grade ≥3 fatigue/asthenia that resolves to Grade ≤2 within one week.
 - Grade 3 anorexia or constipation.

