 - IRRs are not considered to be DLTs because, on the basis of experience with mAbs, IRRs are not dose-related events. Hence, IRRs that require removal of participants from the study will be considered as treatment limiting toxicities and not DLTs. Precautions, including pre-medication, will be taken if IRRs of Grade≥2 occur. If described precautions are not sufficient, other options will be discussed between the Sponsor and the Investigator (see Section 8.3.8.1). However, re-occurrence of an IRR event in a participant that precluded the administration of the full dose or the administration of the next scheduled dose of study drug will be considered a DLT. If clinical judgment suggests that an IRR is related to dose (e.g., driven by on-target mediated release of cytokines by immune cells), a Grade 3 or Grade 4 IRR may be considered a DLT.
 - Grade 3 fever (in the absence of any clinically significant source of fever) that resolves to Grade ≤ 2 within 7 days with supportive care.
 - Fever>40°C (i.e., Grade 3) that occurs within 48 hours of RO7121661 infusion and improves to ≤40°C (Grade ≤2) within 48 hours and fully resolves within one week.
 - Grade 3 arthralgia that can be adequately managed with supportive care or that improves/resolves to Grade ≤ 2 within one week.
 - Grade 3 diarrhea, colitis, enteritis that resolves to Grade ≤ 1 within one week with no fever or dehydration.
 - Laboratory values of Grade ≥ 3 that is asymptomatic and that are judged not clinically significant by the Investigator.
 - Grade 3 tumor pain that starts within 24 hours of infusion and improves/resolves to Grade ≤ 2 within one week.
 - Grade 3 tumor flare defined as local pain, irritation, or rash localized at sites of known or suspected tumor.

- Grade 3 neuropathy if the participant began therapy with a Grade 2 neuropathy at baseline.
- Grade 3 hypoxia that starts within 24 hours of infusion and improves/resolves to Grade ≤ 2 within one week.
- In participants with lung lesions, Grade 3 transient dyspnea secondary to localized lung edema that starts within 24 hours of infusion and resolves to Grade 1 or baseline within one week, and transient bronchospasm that resolves within 24 hours.
- In participants with liver lesions, Grade 3 transient increase of bilirubin, transaminases (aspartate aminotransferase [AST]/alanine aminotransferase [ALT]) and/or gamma-glutamyl transferase (GGT) that starts within 24 hours of infusion and recovers to Grade 1 or baseline within one week.

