From the data available from Part A of this study, a dosing regimen of 2.1 g Q2W was selected as the dose for Part B expansion cohorts. This was based on RO7121661 being well tolerated in the patients dosed in Part A where no specific safety concern associated with RO7121661 was identified. One DLT (Grade 3 Troponin T increased) was observed at the 1200 mg dose group, however no MTD was identified.

A two compartmental PK linear model predicts the exposure data well, particularly at the higher dose range and supports a dose of 2.1 g at Q2W for further investigation. A dose regimen of 2.1 mg QW is predicted to result in a trough concentration of >320 μ g/mL, the predicted EC95 from an ex vivo SEB cytokine assay, in 62% of patients. The dose and regimen may be optimized based on ongoing exposure-response analysis.

The supporting data for the RDE from Part A can be found in the current RO7121661 Investigator's Brochure.

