4. ABNORMAL LABORATORY VALUES

Not every laboratory abnormality qualifies as an adverse event. A laboratory test result should be reported as an adverse event if it meets any of the following criteria:

- Accompanied by clinical symptoms.
- Results in a change in study treatment (e.g., dosage modification, treatment interruption, or treatment discontinuation).
- Results in a medical intervention (e.g., potassium supplementation for hypokalemia) or a change in concomitant therapy.
- Clinically significant in the Investigator's judgment.

It is the Investigator's responsibility to review all laboratory findings. Medical and scientific judgment should be exercised in deciding whether an isolated laboratory abnormality should be classified as an adverse event.

If a clinically significant laboratory abnormality is a sign of a disease or syndrome (e.g., alkaline phosphatase and bilirubin 5 times the upper limit of normal [ULN] associated with cholecystitis), only the diagnosis (i.e., cholecystitis) should be recorded on the Adverse Event eCRF.

If a clinically significant laboratory abnormality is not a sign of a disease or syndrome, the abnormality itself should be recorded on the Adverse Event eCRF, along with a descriptor indicating if the test result is above or below the normal range (e.g., "elevated potassium", as opposed to "abnormal potassium"). If the laboratory abnormality can be characterized by a precise clinical term per standard definitions, the clinical term should be recorded as the adverse event. For example, an elevated serum potassium level of 7.0 mEq/L should be recorded as "hyperkalemia".

Observations of the same clinically significant laboratory abnormality from visit to visit should not be repeatedly recorded on the Adverse Event eCRF, unless the etiology changes. The initial severity of the event should be recorded, and the severity or seriousness should be updated any time the event worsens.

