Appendix 4 Clinical Laboratory Tests

The tests detailed in Table 1 will be performed by the local laboratory unless otherwise specified.

Protocol-specific requirements for inclusion or exclusion of participants are detailed in Sections 5.1 and 5.2, respectively, of the protocol.

Additional tests may be performed at any time during the study as determined necessary by the Investigator or required by local regulations.

All study-required safety laboratory assessments will be performed by local laboratories, with the exception of the following:

• Analysis of IgE and tryptase samples will be performed centrally and locally.

 Table 1
 Protocol-Required Safety Laboratory Assessments

Laboratory Assessments	Parameters
Hematology	Leucocytes, erythrocytes, hemoglobin, hematocrit, platelets, differential count (neutrophils, eosinophils, basophils, monocytes, lymphocytes, other cells).
Clinical Chemistry	Sodium, potassium, chloride, bicarbonate, glucose, urea or BUN, creatinine, protein, albumin, phosphate, calcium, total and direct bilirubin, alkaline phosphatase, ALT, AST, urate, LDH, CRCL (determined by Cockcroft Gault formula) ^a , GGT, Magnesium, CRP, ferritin.
Coagulation	Including PT (optional), INR, and aPTT; additional coagulation parameters (i.e., anti thrombin III [antigenic or chromogenic], fibrinogen, PT, fibrin degradation products, D dimer) maybe be assessed according to clinical judgment.
Viral Serology	HIV (specific tests HIV-1 antibody, HIV-1/2 antibody, HIV-2 antibody), hepatitis B surface antigen (HBsAg), total hepatitis B core antibody (HBcAb), hepatitis C virus (HCV) antibody.
Lipids	Cholesterol, LDL cholesterol, HDL cholesterol, triglycerides.
Thyroid Hormones	Free T4, free T3, TSH
Infusion related reactions	IgE and tryptase and cytokine samples will be collected for central and local analysis if a participant experiences a Grade≥2 IRR for the first time with the second or subsequent study drug infusion or with clinical signs of hypersensitivity reaction at any time of the conduct of the study. A second sample for central IgE/tryptase analysis will be collected approximately 48 hours after onset of the reaction.
Quantitative Immunoglobulins	lgA, lgG, lgM, lgE
Urinalysis	Specific gravity Dipstick: pH, glucose, protein, blood, ketones, bilirubin, urobilinogen, nitrite, leukocyte esterase

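### Part A's only reported DLT was a Grade 3 troponin T increase, yet Part B schedules no troponin, so it cannot give a rate for that signal or show whether a later elevation is new

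*Combined protocol and SAP*

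**What the plan says.** Section 2.3 states that in Part A "1 DLT (Grade 3 Troponin T increased, unresolved at the time of the publication of this version of protocol) was observed" at the 1.2 g dose level. Section 4.4 repeats the finding: "One DLT (Grade 3 Troponin T increased) was observed at the 1200 mg dose group, however no MTD was identified". Under Section 4.1.3 a DLT must be judged related to the drug, must not be attributed to progression or another clear cause, and must be an event "occurring during the DLT assessment period of 21 days from the start of the first RO7121661 administration". A laboratory value of Grade 3 or higher "that is asymptomatic and that are judged not clinically significant by the Investigator" is exempt, and this one was not exempted.

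The chemistry row of Appendix 4 Table 1 includes "albumin, phosphate, calcium, total and direct bilirubin, alkaline phosphatase, ALT, AST, urate, LDH" and ends with creatinine clearance, GGT, magnesium, CRP and ferritin. It has no troponin or creatine kinase. The row for other tests holds only sCD25. Neither Table 1 nor the Part B hourly schedule (Table 3) has a troponin row. The word troponin occurs only in the two descriptions of the DLT.

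There are two other routes to a test. Appendix 4 says "Additional tests may be performed at any time during the study as determined necessary by the Investigator", and Appendix 6 asks for cardiac enzymes in patients with possible myocarditis. Section 8.2.6 requires unscheduled local results to be recorded (in the AE form) only if they change management or are judged clinically significant. Appendix 3, Section 4 adds: "Not every laboratory abnormality qualifies as an adverse event".

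**The concern.** Expansion cohorts are where a toxicity seen once in escalation can be measured in more people. The one dose-limiting signal reported from Part A is a laboratory value, and Part B does not schedule that laboratory test. Three things follow.

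- **No denominator.** Those tested will be chosen because of symptoms or local habit, and normal results need not be recorded. Neither a rate nor an upper limit can be calculated.
- **No protocol-required baseline.** Participants with NYHA class up to 2 are eligible. Without a screening value, an elevation found later cannot be classed as new or pre-existing.
- **No trigger in someone without symptoms.** Appendix 6 accepts a laboratory abnormality as grounds to suspect myocarditis, but no cardiac marker is scheduled that could produce one.

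An absence of troponin reports in Part B would therefore not show that elevations are rare.

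**Working it through.** **Check on a stated figure.** Section 2.3 gives an "overall disease control rate (DCR) of 35.9% (14/39 patients"): 14/39 = 0.359, which agrees. The plan states no rate, power or precision for troponin, so there is no figure of its own to reproduce. Section 9.2 says the sample sizes do not reflect explicit power or Type I error considerations.

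**What Part A shows.** The number tested for troponin is not stated. For one case in n tested, the exact (Clopper-Pearson) 95% interval runs from 1 − 0.975^(1/n) to the 97.5% point of Beta(2, n − 1).

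| Tested (assumed) | Rate | 95% interval |
|---|---|---|
| 39 | 2.6% | 0.1% to 13.5% |
| 20 | 5.0% | 0.1% to 24.9% |
| 10 | 10.0% | 0.3% to 44.5% |

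**Size of Part B.** The cohort sizes are redacted. Section 9.2 gives 270 to 280 in total, and Appendix 10 caps escalation at 60. So 270 − 60 = 210 and 280 − 60 = 220, or 42 to 44 in each of five cohorts if they are equal. These are ceilings, because any additional Part A participants (number also redacted) would come off them. Rounded values of 200 and 40 are used below.

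**What zero reports would mean.** Let r be the true rate of elevation without symptoms and f the share of such participants who happen to be tested. Then P(none detected) = (1 − r·f)^n. With r = 5% (assumed):

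| f (assumed) | n = 200 | n = 40 |
|---|---|---|
| 0 | 100% | 100% |
| 5% | 0.9975^200 = 61% | 0.9975^40 = 90% |
| 10% | 0.995^200 = 37% | 0.995^40 = 82% |
| 20% | 0.99^200 = 13% | 0.99^40 = 67% |
| 100% (scheduled) | 0.95^200 = 0.0035% | 0.95^40 = 13% |

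The first row holds whatever value r takes. If nobody without symptoms is tested, zero reports fit any rate.

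**What scheduled testing would give.** For zero elevations among n tested, the one-sided 95% upper limit is 1 − 0.05^(1/n), which is 7.2% for n = 40 and 1.5% for n = 200.

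**Timing of the proposed draws.** Day 1 of Cycles 1 to 5 falls on Days 1, 15, 29, 43 and 57 if no dose is delayed. That spans the 21-day DLT window and 57 − 21 = 36 further days.

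**The case against.** The strongest reply is that the plan never sets out to estimate a troponin rate. Part B's safety endpoint is the incidence, nature and severity of adverse events, reported descriptively, and zero reports fail to bound the rate of any unscheduled analyte. Amylase and lipase are also missing from Appendix 4, although Appendix 6 has graded actions for them. The sponsor states that no specific safety concern was identified, reports no DLT at 2.1 g, and refers the supporting data to the Investigator's Brochure, which is not available here. Triplicate ECGs are scheduled every cycle. The Joint Monitoring Committee reviews clinically significant laboratory abnormalities. A measured troponin rise can be reported as an adverse event without symptoms if the investigator judges it clinically significant.

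Much of this stands as a limit on the point. It does not remove it, because none of these safeguards measures troponin. What sets this analyte apart is that it produced the only reported DLT.

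Four stronger readings are tempting, and the documents do not support them:

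- **That the Part A case was silent.** The documents do not say how it was found or whether there were symptoms. Its non-exemption, and the listing in Section 4.1.3 of laboratory abnormalities needing treatment or hospitalization as DLTs, suggest clinical relevance, though neither settles the matter.
- **That 2.1 g carries more risk than 1.2 g.** One event cannot show a dose relation.
- **That Part B leaves cardiac toxicity unmonitored.** Symptomatic cases have a clear route to detection.
- **That the detection probabilities are forecasts for this trial.** The rate, the share tested and the cohort sizes are all assumed.

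**Conclusion.** The point holds as a gap in monitoring and in data capture. Part B, as scheduled, cannot give a rate for the laboratory signal behind Part A's only reported DLT, and it has no protocol-required baseline against which to class a later elevation. This conclusion rests on the schedules, Appendix 4 and Section 8.2.6, and needs none of the assumed inputs.

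The size of the underlying risk is unknown. The Part A intervals together run from 0.1% to 44.5%, depending on how many were tested. The detection probabilities only illustrate how little an absence of reports would mean. This version's schedule omits troponin for Part A as well, and whether a previous protocol version included it cannot be told. The laboratory manual was not available, but Appendix 4 is the protocol's own list of required safety tests. The change is worth making because it is cheap and serves Part B's stated aim.

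**What to change.** For Part B participants not yet dosed:

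1. Add troponin to the Appendix 4 chemistry panel at screening and at the pre-dose Day 1 chemistry draws of Cycles 1 to 5 already in Table 3. Use the same local assay throughout for each participant, and record the local upper limit of normal.
2. Enter every result in the eCRF, normal ones included.
3. Add troponin to the Table 9 shift tables, by CTCAE grade or multiple of the upper limit, with the number tested as denominator.
4. State the action threshold. A value newly above the local upper limit, or a prespecified rise over an abnormal baseline, prompts a repeat troponin, an ECG and clinical review before the next dose. The full Appendix 6 myocarditis work-up follows only if the elevation is confirmed or other findings are present.

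The cost is one analyte on five or six existing draws (five if screening falls within 72 hours of Cycle 1 Day 1) and no new visit. Some incidental elevations will need follow-up, a few may lead to cardiology work-up, and a dose may occasionally be delayed. A baseline cannot be recovered for anyone already treated, so the number tested may fall short of the full cohort. Onset after Cycle 5 would still depend on symptoms or investigator judgment.
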